Active Powered Prosthesis (APEX) for Spinal Cord Injury

Protocol #6100003-100 Rev A

Study Sponsor: AbiliTech Medical Inc. & The National Institutes of Health (R43HD094440)

Principal Investigator:	[name], MS, OT/L Program Coordinator for Spinal Cord Injury Program and Research Clinician, Courage Kenny Rehabilitation Institute
Clinical Supervisor:	[name], DO Medical Director, Spinal Cord Injury Rehabilitation, Courage Kenny Rehabilitation Institute
Co-Investigator:	[name], OTR/L Occupational Therapist, Instructor Scientist, Assistive Technology Supervisor
Engineering Director:	[name], MS VP R&D, AbiliTech Medical
Abilitech Clinical Director:	[name]. Clinical and Product Manager, AbiliTech Medical
Design Req Specialist:	[name], BS CEO and President, AbiliTech Medical
Technical Specialist:	[name]. Lead Software Engineer, AbiliTech Medical
Research Project Manager:	[name], BS Project Manager, AbiliTech Medical

Courage Kenny Rehabilitation Institute
Allina Health
[name]
[name]

Protocol Synopsis

Introduction

The Active Powered Prosthesis (APEX) (AbiliTech Medical Inc., Minneapolis, MN) is a proof-of-concept shoulder-elbow-wrist prosthesis device intended to provide non-invasive active powered robotic assistive movement to the upper extremities. In September 2017, the National Institutes of Health approved and funded the development of the APEX device through a Phase I SBIR Grant.

(1R43HD094440-01). The APEX device is designed for users with upper level cervical spinal cord injuries and motor impairment of their upper extremities. AbiliTech Medical has a history of developing upper extremity prosthesis devices. The AbiliTech Assist device is an upper limb passive powered lift and assist device planned for release in Q3 2018. The APEX device represents an advancement from the AbiliTech Assist device by providing active power sources to lift and rotate the upper limbs. The increased range of motion provided by the APEX device will expand the activities of daily living (ADL's) for users of the APEX device.

Study Objectives

Objectives:

Perform focus groups with subjects and clinicians to evaluate a proof of concept active powered prosthesis.

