1.2. AbiliTech Medical APEX Background

The Active Powered Prosthesis (APEX) is a portable upper extremity prosthesis device that helps users with upper extremity motor impairment move their upper extremities through active robotic assistance. The device is controlled through body motion activation (i.e.: a body mounted 9 degree of freedom accelerometer sensor that is wirelessly connected to the device to interpret the user's movement into upper extremity assisted movement). The APEX device body chassis is worn by the user and has onboard processing, power, motors, sensors, and cables attached to the motors . Cables attached to the motors will extend throughout the body chassis to enable actuation of the user's upper extremities. The APEX is designed for optimal subject safety including mechanical, electrical and software stops to prevent uncontrolled device movement and injury to subjects.

Arm movement is activated and controlled by the APEX control system (ACS-III) consisting of body mounted movement control inputs and sensors, an on-board processor, sensors, motors, and firmware. While the APEX mechanical design is the initial concept model, the ACS III control system represents a third-generation control and data collection design. User directed control inputs will be

body motion activated, sensors will be placed on the head and/or combination of a head mounted joystick and buttons.

This is a first of its kind proof-of-concept model using a mobile Bowden-Cable robotic system to mobilize the upper extremity. A similar published research device called the CAREX [19] has demonstrated proof-of-concept but is stationary and has limited data on its use.

AbiliTech Medical has experience in developing similar devices. The AbiliTech Assist and the Hand Grip glove, funded by the State of Minnesota Spinal Cord and Traumatic Brain Injury Research Grant Program, are devices currently in development by AbiliTech Medical. The AbiliTech Assist is a hybrid power device. Motors power (active) the compression or relaxation of multiple arm and shoulder springs (passive) to provide lift and assist for users with reduced upper extremity mobility. The AbiliTech Hand Grip System, uses motors and cables to help users grasp and hold different objects and is similar in cable driven architecture to the APEX device. The APEX device will be a third-generation device leveraging the design architecture eg. ACS-III and clinical learning experience.

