1: Consent (Up to 30 minutes)	1.1: Review and Sign Informed Consent Form (0-30 minutes)	Study participants will review and sign consent form in a group setting. They will be given time as to review and provide consent. Consent forms will be mailed to scheduled participants in advance of the focus group session.
2: Device Testing and Follow up (approximately 90 minutes)	2.1: Device Instructions and Operational Testing (60 minutes)	The clinician and AbiliTech Personnel will describe to the user on how to operate the device. The study participant will acclimate to use of the device. Data will be collected on the operation, function, and performance of the APEX device. Safety risks will be assessed.

	2.2: Device & Follow Up (10-15 minutes)	The study participant will provide feedback about their experience with the device.
3: Device Feedback (approximately 30-60 minutes)	3.1 Complete Survey	Subject performs Survey Monkey Survey on Device Preferences. Compensation provided upon survey completion.

Part 2 of the study will comprise of a clinician focus group to evaluate data gathered in the user focus group, AbiliTech bench testing, and motion capture data of the device function. Appendix 5 includes questions for clinicians to answer. Table 2 highlights the Clinician focus group activities.

Table 2: Visit 2: Clinician Focus Group Activities

	Activity	Description
1: Data Review (approximately 60 minutes)	1.1: Study Data Presentation	AbiliTech Medical will present data to CKRI clinical team. Data includes User focus group results and results device bench testing.
2: Device Feedback (approximately 60 minutes)	2.1 Discussion on Device	Clinicians and AbiliTech Medical team members will discuss the safety and clinical utility of the APEX device.

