In compliance with the ICH/GCP guidelines the investigator will maintain all CRFs and all source documents that support the data collected from each subject, and all trial documents as specified in Essential Documents for the Conduct of a Clinical Trial and as specified by the applicable regulatory requirement(s). The investigator will take measures to prevent accidental or premature destruction of these documents. Essential documents will be retained until at least two years after the last approval of a marketing application in an ICH region or at least two years have elapsed since the formal discontinuation of clinical development of the investigational product. These documents will be retained for a longer period if required by the applicable regulatory requirements or by an agreement with the sponsor. These documents will be retained for a longer period if required by Abbott Northwestern Hospital policies and procedures.

Original documents will be secured in a locked cabinet in the Courage Kenny Research Center. Copies that do not identify the study participant human subjects (using a code such as AMI-CKRI-XXX) may be shared with AbiliTech Medical for data and evaluation. AbiliTech will store the data in a locked cabinet on company premises with restricted access. Electronic copies with de-personalized data may be analyzed in an excel file. De-identified survey results will be collected and stored in Survey monkey web application for data analysis. Audio recordings will be transcribed and de-identified. Video recordings will be of device function and not of focus group participants.

10. Amendments to the Protocol

All protocol amendments will be submitted to the IRB. Amended protocol will be reviewed, approved and documented by the same method as the original protocol was reviewed and approved. Once the amended protocol and all associated documents are reviewed and approved, the most recent protocol version and effective date will be changed on all pages of the protocol. Study personnel will be notified of any protocol deviations.

11. Deviations from Investigative Plan

The Investigator is not allowed to deviate from the clinical investigation plan. Under emergency circumstances, deviations from the protocol to protect the rights, safety and well-being of human subjects may proceed without prior IRB. Such deviations shall be documented and reported to the IRB as soon as possible.

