Appendix 2: Pilot Usability Testing Form

[name]
[contact] www.abilitechmedical.com

AbiliTech Medical APEX Study Pilot Usability Testing Form

Subject Information

Subject ID Number _____

Subject Assessment with APEX

Is the subject familiar with smartphone applications? Yes No

Can the subject use voice control features of the application to toggle between device modes? Yes No

Can the subject use the head worn accelerometer to control the APEX device movement? Yes No

Can subject power the device on/off? Yes No

Can the subject move the APEX on a mannequin in the following Ranges of Motion?

Shoulder

Flexion Powered ROM: 0 to 60° Yes No

Shoulder Abduction Powered ROM: 0 to 30° Yes No

Horizontal Internal Rotation Powered ROM: 35 to -35° Yes No

Compound Shoulder ROM (Flexion, internal rotation, horizontal adduction: limited in horizontal plane): 0 to 100° Yes No

Elbow

Elbow Flexion/Extension Powered ROM: 0 to 130° Yes No

Forearm

Supination Powered ROM: 0 to 60° Yes No

Pronation Powered ROM: 0 to 50° Yes No

Can the subject move the APEX on a mannequin to complete the following tasks?

Control APEX device to manipulate objects in space Yes No

Control APEX to move an object in a preferred pathway Yes No

Control APEX device to push buttons Yes No

Control APEX to lift a water bottle from table level Yes No

Control APEX to lift a phone Yes No

Uncontrolled device movement observed: Yes No (if yes, please comment below)

Time spent using the device: _____ (min)

Notes

Utility

1. On a scale of 1 to 5, how would the APEX System improve your ability to use your arms? (1 no improvement - 5 strong improvement)
2. In general, what would you like to be able to do with your arms?
3. What are three to five Activities of daily living that you wish you could perform, listed in priority?
4. Do you think using the APEX device you could do [each of the ADL they stated]?

Device Feedback

1. What is your general impression of the APEX System, knowing the development phase it is in?
2. Would you use the APEX System? How much? Where? When? For what Uses?
3. What do you like about the APEX System?
4. What do you dislike about the APEX device?

5. What could be improved about the APEX device?
6. What is your opinion about the size, appearance, texture, color, and/or noise of the APEX device?
7. What is your opinion on the control system?
8. What type of control system would you prefer?

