Appendix 4: AbiliTech Medical APEX Device Feedback Questions

[name]
[contact] www.abilitechmedical.com

AbiliTech Medical APEX Device Subject Device Survey Questions

APEX Survey Monkey Questions

[figure not shown]

1. What is your gender?
 											

2. What is your age?
 
 18-29 years old
 
 30-49 years old
 
 50-64 years old
 
 65 years and over
											

3. How long ago was your injury?
 

 less than 6 months	 5- 10 years ago	

 6 months to 1 year ago	 10-20 years ago	

 1 - 2 years ago	 25+ years ago	

 2 - 5 years ago		

		 less than 6 months	 5- 10 years ago	 6 months to 1 year ago	 10-20 years ago	 1 - 2 years ago	 25+ years ago	 2 - 5 years ago			
 less than 6 months	 5- 10 years ago										
 6 months to 1 year ago	 10-20 years ago										
 1 - 2 years ago	 25+ years ago										
 2 - 5 years ago											

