51. I would use this device for X hours a day

- 1-2 hours
- 2-4 hours
- 4-6 hours
- 6+ hours

52. If this device were useful to me and insurance would not cover it, the maximum amount I would pay for a hand grip device would be...

- \$1,000
- \$10,000
- \$2,500
- I would not pay for this
- \$5,000

53. How long should the battery last until it needs to be recharged?

- 4 hours
- 8 hours
- 24 hours
- 48 hours

54. Other than lack of voluntary movement, do you have any limitations that would prevent finger or hand movement?

55. Do you have any safety concerns for this device?

56. If safety concerns, please comment.

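### Survey question 51 cannot record non-use or use under one hour a day, and question 52 leaves unclear which device is being priced

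*Combined protocol and SAP*

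**What the plan says.** Section 2 lists subject-reported outcomes as primary outcome 5, collected through interviews and a survey. The survey is Appendix 4, headed "AbiliTech Medical APEX Device Subject Device Survey Questions". Three features of it matter here.

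- **Question 51** reads "I would use this device for X hours a day". Its options are 1-2, 2-4, 4-6 and 6+ hours, with no zero, under-one-hour, not-applicable or free-text choice.
- **Question 52** reads "If this device were useful to me and insurance would not cover it, the maximum amount I would pay for a hand grip device". Its options run from $1,000 to $10,000, with a choice to decline to pay.
- **Question 3**, on time since injury, goes from a 10-20 year option to a 25+ year option.

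The Synopsis introduces APEX as a "proof-of-concept shoulder-elbow-wrist prosthesis device". Section 1.2 describes another sponsor product: "The AbiliTech Hand Grip System, uses motors and cables to help users grasp and hold different objects".

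Table 1 in Section 4 says of the survey: "Compensation provided upon survey completion". Section 9 says: "De-identified survey results will be collected and stored in Survey monkey web application for data analysis". In the interview, Device Feedback question 2 (after the Appendix 2 form) asks "Would you use the APEX System? How much? Where? When? For what Uses". Section 8 plans no statistical analysis, because only 3 to 6 subjects will take part.

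**The concern.** Non-use is a plausible answer. Subjects will only have operated a proof-of-concept prototype on a mannequin, and the interview itself asks whether they would use it. Question 51 has nowhere to put that answer. Other items in the same survey do provide a null answer: question 19 (no pain), question 39 (never used) and question 52 (would not pay). The gap therefore looks like an oversight. Payment on completing the survey gives some reason to tick a box rather than skip, although the documents do not say whether items may be skipped.

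Question 52 starts with the device under discussion and ends with a hand grip device. A respondent may price APEX, the hand-grip product, or a general idea of either.

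Section 4 says the study will inform customer and design requirements for a commercial APEX. That expected daily use and price belong among those requirements is an inference, since neither is a named outcome or feasibility criterion. If they are used that way, question 51 would show every respondent at one hour or more whatever their true view, and question 52 would give a price for an uncertain product.

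**Working it through.** The plan states no figure on this point, so there is nothing to reproduce.

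**Inputs.** The question 51 and 52 options come from Appendix 4, and n = 3 to 6 from Sections 3, 4 and 8. Assumption: one subject's true use is *t* hours a day, with 0 ≤ *t* < 1. If there is no such subject, the missing floor changes nothing.

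**1. Share of the sample affected, 1/n.** 1/3 = 33.3%, 1/4 = 25.0%, 1/5 = 20.0%, 1/6 = 16.7%.

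**2. The subject picks the lowest band, 1-2 hours.** The overstatement lies between 1 − *t* and 2 − *t*. Since *t* < 1, the lower limit is above 0. Since *t* ≥ 0, the upper limit is at most 2 hours.

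**3. The subject leaves the item blank.** The item then shows n − 1 = 2, 3, 4 or 5 answers, all at one hour or more, and the blank looks like ordinary non-response.

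**4. Group picture (illustration only; no mean or percentage is planned).**

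- The true share at one hour or more is (n − 1)/n: 2/3 = 67% at n = 3, 5/6 = 83% at n = 6. Question 51 shows 100% of those who answer.
- A complete non-user (*t* = 0) placed in 1-2 hours raises the group mean by 1/n to 2/n hours: 0.33 to 0.67 at n = 3, 0.17 to 0.33 at n = 6.
- All answer patterns at n = 3 and n = 6 with at least one subject below an hour were enumerated. Assumed values were 0 or 0.5 hours below the floor and 1.5, 3, 5 and 7 hours for the four bands. With the lowest box chosen, the mean is overstated by 0.33 to 1.5 hours (n = 3) or 0.17 to 1.5 hours (n = 6). With the item skipped, the mean of those who answer is too high by at least 0.33 or 0.17 hours. No pattern gave a downward error. The sizes depend on the assumed values; the direction does not.

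**5. Band edges.** The internal boundaries 2, 4 and 6 are each shared by adjacent bands (3 of 3). The open top band could understate heavy use, but that is separate from the missing floor.

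**6. Question 52.** The documents hold 56 survey questions, 4 + 13 = 17 interview questions and 8 clinician questions: 56 + 17 + 8 = 81. Only question 52 asks a device price, so no other answer can resolve it. By contrast, two questions ask about expected use: question 51 and the interview item. The direction and size of any error in question 52 are unknown.

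**7. Question 3.** The gap is 25 − 20 = 5 years.

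**The case against.** The strongest reply is that nothing planned depends on these items. Section 6 judges feasibility on intentional control of the mannequin device, on user feedback about performance, controls and comfort, and on clinician feedback. Hours and price are not among these. Much of the survey is background, such as insurance and transport, and being in the survey does not make an item a primary measure. This stands, and it limits the importance of the point.

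The interview question names APEX, is open-ended and can record non-use. That also stands, and for a small focus group it offsets much of the question 51 problem. It does not repair the survey answer itself. Survey results are de-identified and the survey text shows no subject ID, so matching a subject's two answers is not shown to be possible. The form may carry a code that the text does not show, but the plan does not say so. The interview asks no price.

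For question 52, the APEX heading and the opening words allow an APEX reading, and other survey items on grip and fingers make a hand-grip price a possible intention. Either could be right, and that is the ambiguity.

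Two smaller items deserve little weight. Question 48, on help with putting on a hand-based device, may be meant as written, because mannequin tests 1 and 2 allow a grip device. Appendix 1 records year of injury, so the question 3 gap does not lose that fact from the study, only from the survey.

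**Conclusion.** The concern holds. As written, question 51 moves anyone below one hour a day upward or drops them; it cannot record them. On the assumption of one such subject, this affects 17% to 33% of the sample, with an overstatement above 0 and at most 2 hours a day if they choose the lowest band. With no such subject the effect is nil. Question 52 names two devices in one sentence, so its price cannot be cleanly assigned to APEX.

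The consequence is modest and descriptive. No test, threshold or feasibility criterion uses either item. The edit is still worth making before first use, because the survey is one of two instruments for a primary outcome and, with no statistical analysis planned, individual answers are the result.

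**What to change.** Before the survey is first used, submit these wording edits to the IRB:

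- **Question 51:** name APEX and offer *I would not use it*, *less than 1 hour*, *1 to less than 2*, *2 to less than 4*, *4 to less than 6*, and *6 or more hours*.
- **Question 52:** name APEX as the device being priced. If a hand-grip price is also wanted, ask it as a separately labelled item.
- **Question 3:** change the last two bands to *10 to less than 20* and *20 or more* years, so that the survey does not rely on Appendix 1 to fill the gap.
- **Question 48 (optional):** state which device is meant, and keep the hand-device question if it is wanted.

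If the survey has already been used, report question 51 beside the interview answers on use at group level, and label question 52 as referring to an ambiguous device.

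The cost is a few edits to an online form and possibly one or two extra items on a 56-question survey with a 30-60 minute slot. If the edits are handled as a protocol amendment, Section 10 also requires review and approval by the original method and an updated version and effective date on every page.

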Appendix 5: AbiliTech Medical APEX Device Clinician Feedback Questions

[name]
[contact] www.abilitechmedical.com

AbiliTech Medical APEX Device Clinician Feedback Questions

APEX Study Questions

1. Are there features that should be integrated into the device to enhance clinical utility?

2. Do you have any safety concerns for the use of this device?

3. Do you have feedback on how safety mechanisms can be improved?

4. How would this device benefit your patients?

5. What motions or activities of daily living would be most meaningful for your patients?

6. What type and intensity of training and acclimation would you like to work with your patients for this device?

7. Are you interested in monitoring subject compliance with device?

8. What improvements of the device would you suggest?
